8.3.5 Balance of Circulating CD8⁺ Effector Cell Subpopulation

Given that the antigen spectrum for a given tumor is usually incomplete, it is possible that *neo* antigens could be generated and released from tumor cells following RT, which would not be identified by commercially available tetramers. Since the establishment of antigen specificity for the entire T-cell population is not possible, this study will ascertain whether the antigen burst and/or inflammatory factors released following RT would selectively expand or reduce T cell subpopulation. While RT-induced changes are initiated locally at tumor sites, RT can impact the systemic immune system as observed in the abscopal effect. We hypothesize that tumor antigens and/or inflammatory factors released from RT-induced tumor cell necrosis will trigger an efflux of effector or memory T cells in the peripheral blood since these subpopulation of T cells are antigen-primed and may have a rapid response to altered antigen stimulation in context with inflammatory cytokines. It has been reported that RT increases the serum levels of IL-1beta and IL-6 and reduces the serum levels of TGF-beta in prostate cancer patients after 1-2 weeks of RT. Among the cytokines, IL-6 is responsible for expansion of effector memory CD8⁺ T cells and IL-1beta and TGF-beta regulate the transmigration or tissue retention of effector and memory CD8⁺ T cells. In this portion of the project, fluctuations in frequencies among naïve ($CCR7^+CD45RA^+$), central memory ($CCR7^+CD45RA^-$), effector/effector memory ($CCR7^-CD45RA^-$), and terminally differentiated ($CCR7^-CD45RA^+$) CD8⁺ T cells will be determined and

evaluated together with the development of anti-gastric cancer immunity in relation to the timing of RT. PBMCs and plasma will be isolated at (baseline), after RT (day 8, 15, pre-surgery), after adjuvant therapy, and at tumor recurrence. Cells will be co-stained with antibodies for CD3, CD8, CD45RA, CCR7 to identify CD8⁺ T cells and their phenotype. The percentage of each subset will be determined based on the total CD8⁺ T cells when analyzed by flow cytometry. We will compare the frequency of each subset of CD8⁺ T cells and their PD-1 expression in relation to the different time points following RT. If we identify any significant changes of T cell subset, we will measure the cytokine profiles of these patients at that time point using multiplex methods.

8.3.6 BIM Expression in Circulating T Cells and Tumor-Infiltrating Lymphocytes

The [name] lab recently reported that Bim is a downstream signaling molecule of the PD-1 pathway, and its detection in T cells is significantly associated with expression of PD-1 and effector T cell markers ([Dronca et al., 2016](#)). High levels of Bim in circulating tumor-reactive (PD-1⁺CD11a^{hi}CD8⁺) T cells were prognostic of poor survival in patients with metastatic melanoma who did not receive anti-PD-1 therapy and were also predictive of clinical benefit in patients with metastatic melanoma who were treated with anti-PD-1 therapy. Moreover, this circulating tumor-reactive T cell population significantly decreased after successful anti-PD-1 therapy. This study supports a crucial role of Bim in both T cell activation and apoptosis as regulated by PD-1 and PD-L1 interactions in effector CD8⁺ T cells. Measurement of Bim levels in circulating T cells of patients with cancer may provide a less invasive strategy to predict and monitor responses to anti-PD-1 therapy. This lab also has experience evaluating BIM/PD-1 expression in tumor infiltrating T cells using double-stained IHC.

8.3.7 Expression Profiling to Identify Tissue of Origin in CUP

Accurate identification of the tissue of origin (TOO) via molecular profiling and subsequent site-specific therapy has been theorized to improve outcomes. Gene expression profiling has accurately identified the tissue of origin in ~ 85% of patients in patients with known primary, as a collaborator in the current study ([Kerr et al., 2012](#)) and others ([Erlander et al., 2011](#); [Monzon et al., 2009](#); [Pillai et al., 2011](#)) have shown. In retrospective studies, molecular profiling rendered a prediction in the majority of CUP patients that was consistent with clinical and pathologic features ([Horlings et al., 2008](#); [Varadhachary et al., 2008](#)). In CUP patients whose primary was detected later, molecular testing predicted the primary in 75% of cases ([Greco et al., 2013](#)).

Our group recently found that a commercially available tumor gene expression profiling assay that predicts tissue of origin identified CUP patients who responded to carboplatin/paclitaxel-based chemotherapy ([Yoon et al., 2016](#)). In this multicenter NCI-sponsored cooperative group trial (N0871), patients with a tissue of origin where platinum/taxane is a standard had a higher response rate (53% vs 26%) and significantly longer progression free survival (6.4 vs 3.5 months; HR 0.47; 95% CI 0.24–0.93; $P = .026$) and overall survival (17.8 vs 8.3 months, HR 0.37; 95% CI 0.18–0.76; $P = .005$), compared with patients with a tissue of origin where platinum/taxane is not standard. These data suggest the possible prognostic and predictive importance of evaluating tissue of origin in CUP patients. Multiple commercially available TOO assays (CancerType ID, BioTheranostics; Cancer Genetics) can be ordered for clinical purposes that can aid in diagnosis and treatment decisions. Pre-treatment tissue (archival or biopsy) will be submitted for TOO assay analyses.

8.3 Storage of Biospecimens

At the completion of the study, any unused/remaining material will be stored for future research in the area of cancer. Patients will be asked permission to store leftover samples of tissue or blood.

8.4 Confidentiality of Biospecimens

Samples that are collected will be identified by a subject's sequence ID assigned at the time of registration to the trial. Any material issued to collaborating researchers will be anonymized and only identified by the subject's sequence ID.

9. CRITERIA FOR DISEASE EVALUATION

RECIST 1.1 will be adapted to account for the unique tumor response characteristics seen with treatment of pembrolizumab. Immunotherapeutic agents such as pembrolizumab may produce antitumor effects by potentiating endogenous cancer-specific immune responses. The response patterns seen with such an approach may extend beyond the typical time course of responses seen with cytotoxic agents, and can induce a clinical response after an apparent initial increase in tumor volume or even the appearance of new lesions. Standard RECIST may not provide an accurate response assessment of immunotherapeutic agents such as pembrolizumab. Immune-related RECIST (irRECIST) is RECIST 1.1 adapted as described below to account for the unique tumor response seen with immuno-therapeutics. In addition, an improved long-term survival has been observed when using the best abscopal response as the predictor variable.

The version of RECIST used in this study will be the new international criteria proposed by the revised Response Evaluation Criteria in Solid Tumors (RECIST) guidelines (version 1.1) by Eisenhauer et al. Changes in the largest diameter (unidimensional measurement) of the tumor lesions and the short axis measurements in the case of lymph nodes are used in the RECIST guideline.

9.1 Tumor Imaging and Assessment of Disease

Each participating site will determine subject eligibility and response. All CT, PET, and MRI scans, scheduled and unscheduled, should be submitted to central imaging as soon as possible. Treatment decisions will be based on the site investigator's radiographic assessment of disease, and not based on Research Base's assessment. There will be no real-time confirmation from central review. Retrospectively, the Research Base will review radiologic images for a retrospective analysis of subject eligibility and response.

Tumor imaging may be performed by computed tomography (CT) (preferred) or magnetic resonance imaging (MRI), but the same imaging technique, acquisition, and processing parameters should be used in a subject throughout the trial. Scans performed as part of routine clinical management are acceptable for use as the baseline scan if they are of diagnostic quality. Scans performed as part of routine clinical management are acceptable for use as the baseline scan if they are of diagnostic quality.

Imaging should follow calendar days and not be delayed for any dose interruptions that may occur.

Imaging should continue to be performed until whichever one of the following occurs first:

- disease progression
- start of new systemic anti-cancer treatment
- withdrawal of consent
- death
- end of study

9.1.1 Timing of Repeat Imaging to Confirm Response

Best abscopal response should be confirmed by a repeat radiographic assessment not less than 4 weeks from the date the response was first documented.

9.2 Assessment of Disease

9.2.1 Determination of Response (tumor shrinkage)

Best abscopal response will be applied as the primary measure for assessment of tumor shrinkage, following the NYU study by Golden et al (see Background 1.2.2).

Best abscopal response is defined as either of the following:

- Non-nodal lesions: Decrease in the longest diameter by at least 30% in any measurable (≥ 1 cm) non-irradiated lesion from baseline
- Nodal lesions: Decrease in the short-axis diameter of any measurable (≥ 1.5 cm) non-irradiated nodal lesion from baseline

RECIST 1.1 will be applied as a secondary measure for assessment of tumor response.

9.2.2 Determination of Progressive Disease (irRECIST)

irRECIST is applied only in situations when first radiographic progression per RECIST 1.1 has occurred. After initial radiographic progression per RECIST 1.1, irRECIST will be used by site investigators to assess tumor progression and to make treatment decisions.

If radiologic imaging verifies initial disease progression per RECIST 1.1, treatment may continue at the discretion of the site investigator until repeat imaging ≥ 4 weeks later. The site investigator's decision to continue treatment while awaiting repeat imaging should be based on the subject's overall clinical condition guided by the following criteria:

- Absence of signs and symptoms indicating disease progression
- No decline in ECOG performance status
- Absence of rapid progression of disease
- Absence of progressive tumor at critical anatomical sites (eg, cord compression) requiring urgent alternative medical intervention

Assessment of repeat imaging after initial RECIST 1.1-defined disease progression:

Subject will be considered as not having disease progression as defined by irRECIST if repeat imaging shows:

- $< 20\%$ increase in tumor burden compared to nadir, and
- Stable or improved previous new lesion (if identified as cause for initial disease progression), and
- Stable/improved non-target disease (if identified as cause for initial disease progression).

- *Treatment plan:* Treatment may be continued/resumed.

Subject will be considered as having disease progression as defined by irRECIST if repeat imaging confirms disease progression due to any of the scenarios listed below:

- Tumor burden remains $\geq 20\%$ and at least 5 mm absolute increase compared to nadir, or
- Non-target disease resulting in initial disease progression is worse (qualitative), or
- New lesion resulting in initial disease progression is worse (qualitative), or
- Additional new lesion(s) since last evaluation
- *Treatment plan:* Subjects will be discontinued from study therapy

In determining whether or not the tumor burden has increased or decreased, site investigators should consider all target lesions as well as non-target lesions.

In cases where irRECIST-defined progression is occurring at the same time as a best abscopal response, study treatment should generally be discontinued. However, if the subject is achieving a clinically meaningful benefit, an exception to continue treatment may be considered.

The guidance described above regarding treatment continuation/discontinuation and repeat imaging per irRECIST is described in the table below.

When feasible, study treatment should continue until progression is confirmed. Subjects that are deemed clinically unstable are not required to have repeat imaging for confirmation of progressive disease. Subsequent tumor imaging follows protocol schedule.

Plan for Imaging and Treatment after 1st Radiologic Evidence of Progressive

Plan for Imaging and Treatment after 1st Radiologic Evidence of Progressive Disease (application of irRECIST)				
Scenario	Clinically stable		Clinically unstable	
	Imaging plan	Treatment plan	Imaging plan	Treatment plan
1 st radiologic evidence of PD as defined by RECIST 1.1	Perform repeat scan at ≥ 4 weeks to confirm PD.	May continue study treatment at Investigator's discretion while awaiting repeat scan	Perform repeat scan at ≥ 4 weeks to confirm PD per Investigator discretion only	Discontinue study treatment
Repeat scan confirms PD as defined by irRECIST	No additional scans required.	Discontinue treatment (exception is possible upon consultation with Research Base) ¹	No additional scans required	N/A
Repeat scan shows SD, PR, or CR as defined by irRECIST	Continue regularly scheduled scans.	Continue study treatment at Investigator's discretion	Continue regularly scheduled scans.	May restart study treatment if condition has improved and/or clinically stable per Investigator's discretion

CR = complete response; PD = progressive disease; PR = partial response; SD = stable disease

¹ If a subject has confirmed radiographic progression per irRECIST (i.e., 2 scans at least 4 weeks apart demonstrating progressive disease), but the subject is achieving a clinically meaningful benefit (e.g., experiencing a response in a non-irradiated lesion), an exception to continue treatment may be considered following consultation with the Research Base.

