9.6 Response Criteria per RECIST 1.1

All target lesions and target lymph nodes followed by

- CT/MRI/PET-CT/Chest X-ray/physical examination must be measured on re-evaluation. Specifically, a change in objective status to either a PR or CR cannot be done without re-measuring target lesions and target lymph nodes.

NOTE: Non-target lesions and non-target lymph nodes should be evaluated at each assessment, especially in the case of first response or confirmation of response. In selected circumstances, certain non-target organs may be evaluated less frequently. For example, bone scans may need to be repeated only when complete response is identified in target disease or when progression in bone is suspected.

Evaluation of Target Lesions

- Complete Response (CR): All of the following must be true:
 - Disappearance of all target lesions.
 - Each target lymph node must have reduction in short axis to <1.0 cm.
- Partial Response (PR): At least a 30% decrease in PBSD (sum of the longest diameter for all target lesions plus the sum of the short axis of all the target lymph nodes at current evaluation) taking as reference the BSD.
- Progression (PD): At least one of the following must be true:
 - At least one new malignant lesion, which also includes any lymph node that was normal at baseline (< 1.0 cm short axis) and increased to \geq 1.0 cm short axis during follow-up.
 - At least a 20% increase in PBSD (sum of the longest diameter for all target lesions plus the sum of the short axis of all the target lymph nodes at current evaluation) taking as reference the MSD (Section 11.41). In addition, the PBSD must also demonstrate an absolute increase of at least 0.5 cm from the MSD.
 - See Section 11.1 on incorporation of irRECIST in determining whether PD on RECIST counts as true progression.

- See Section 11.32 for details regarding the requirements for PD via FDG-PET imaging.
- Stable Disease (SD): Neither sufficient shrinkage to qualify for PR, nor sufficient increase to qualify for PD taking as reference the MSD.

Evaluation of Non-Target Lesions & Non-target Lymph Nodes

- Complete Response (CR): All of the following must be true:
 - Disappearance of all non-target lesions.
 - Each non-target lymph node must have a reduction in short axis to <1.0 cm.
- Non-CR/Non-PD: Persistence of one or more non-target lesions or non-target lymph nodes.
- Progression (PD): At least one of the following must be true:

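### Section 9.2.2: the two repeat-scan lists for irRECIST progression overlap when an additional new lesion appears, and leave a narrow gap for rises of at least 20% but under 5 mm

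*Combined protocol and SAP*

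**What the plan says.** Section 9.2.2 limits the rule's reach: "irRECIST is applied only in situations when first radiographic progression per RECIST 1.1 has occurred". Repeat imaging follows at least 4 weeks later, and the site classifies it with two lists.

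- **Not progression.** The list opens "Subject will be considered as not having disease progression as defined by irRECIST if repeat imaging shows". Three conditions must all hold. The first is an under-20% "increase in tumor burden compared to nadir, and" the other two require that the new lesion, or the non-target disease, be stable or improved if it caused the first progression. The attached plan is that treatment may go on or resume.
- **Progression.** Any one of four items is enough: tumor burden that remains up by 20% or more with "at least 5 mm absolute increase compared to nadir, or" worse causal non-target disease; a worse causal new lesion; or "Additional new lesion(s) since last evaluation". The attached plan is to stop study therapy.

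The table in the same section says "Continue regularly scheduled scans" when the repeat scan shows stable disease or response by irRECIST, and requires no further scans when it confirms progression.

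Section 9.6, on RECIST 1.1, has the same floor: "In addition, the PBSD must also demonstrate an absolute increase of at least 0.5 cm from the MSD". It lists as progression "At least one new malignant lesion, which also includes any lymph node that was normal at baseline" (with a node size threshold). Stable disease is whatever qualifies as neither partial response nor progression.

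**The concern.** Both lists are written as binding classifications, with opposite treatment plans. Section 9.2.2 does not rank them, does not say what to do with a scan that meets neither, and does not refer to 9.6. The lists are not mirror images. The progression list has a 5 mm floor and an item on additional new lesions; the other list has neither.

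Sites apply these lists on their own. Section 9.1 bases treatment decisions on the site's reading and provides no real-time central confirmation. The classification bears on whether therapy stops, whether continuing needs consultation with the Research Base (table footnote), whether imaging goes on, and whether the patient moves to event monitoring (9.8.2). Two sites could treat the same scan differently, each with text to cite.

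**Working it through.** The plan gives no derived figure on this point. Its only numbers are the 20% and 5 mm thresholds, so the check is one of logic plus one bound.

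**Notation for the repeat scan**
- R: rise over nadir is at least 20%
- F: rise over nadir is at least 5 mm
- N: non-target disease that caused the first progression is worse
- L: new lesion that caused the first progression is worse
- A: an additional new lesion is present

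**The lists as written**, reading *remains* in progression item 1 as *is*:
- Not progression = (not R) and (not N) and (not L)
- Progression = (R and F) or N or L or A

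**Overlap.** Both hold exactly when R, N and L are all false and A is true: under 20% growth, original cause stable, additional new lesion.

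**Gap.** Neither holds exactly when R is true and F, N, L and A are all false: a rise of at least 20% but under 5 mm, with no other progression item.

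**Bound on the gap.** A rise that reaches 20% but stays under 5 mm needs 0.20 × nadir < 5 mm, so nadir < 5 / 0.20 = 25 mm.

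| Nadir sum | 20% of nadir | Rises meeting neither list |
|---|---|---|
| 10 mm | 2.0 mm | 2.0 to under 5 mm |
| 15 mm | 3.0 mm | 3.0 to under 5 mm |
| 20 mm | 4.0 mm | 4.0 to under 5 mm |
| 25 mm or more | 5.0 mm or more | none |

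**Can it happen?** Yes. Section 3.1 asks for only one measurable lesion outside the RT fields, and Section 9.3.1 accepts 1.0 cm on CT. Example: the nadir is 18 mm. The first progression is at 24 mm: 24 − 18 = 6 mm and 6/18 = 33%, so both RECIST thresholds are met. The repeat scan is 22 mm: 22 − 18 = 4 mm and 4/18 = 22%. With nothing else changed, the repeat scan is in neither list.

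**What the lists should be.** The exact complement of the progression list is (not R or not F) and (not N) and (not L) and (not A). The current first list lacks two pieces of this: *or not F*, and *not A*. Adding only the first closes the gap but leaves the overlap. Adding only the second removes the overlap but leaves the gap.

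**A remaining hole.** Progression item 1 says the tumor burden *remains* above the thresholds. Suppose the first progression came only from a new lesion or non-target disease, that cause is now stable, no further lesion has appeared, and the target sum first crosses 20% and 5 mm on the repeat scan. Read literally, nothing *remains*, so item 1 fails; the rise is at least 20% and at least 5 mm, so the first list fails too. This scan would be in neither list even after both additions, unless that word is changed.

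**The case against.** The strongest reply is that the intended answers can be found. The opening of Section 9 describes irRECIST as an adaptation of RECIST 1.1, so RECIST 1.1 is the base rule wherever 9.2.2 is silent. On that footing:

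- The overlap is progression. The progression list needs only one item and names additional new lesions, 9.6 counts a new malignant lesion as progression, and the table in 9.6.1 gives progression for new disease whatever the target status.
- The gap is stable disease. Progression needs both thresholds, stable disease is the residual category in 9.6, and a scan that meets no progression item triggers no instruction to stop.

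The gap is also narrow, and 9.2.2 allows exceptions for clinical benefit in any case.

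Most of this stands, and it is why the point is minor. It does not remove it. Because irRECIST is presented as an adaptation, a site can fairly take a difference in the 9.2.2 list as the adaptation itself. The table refers to irRECIST stable disease without defining it. The 9.6 pointer on whether RECIST progression counts as true progression goes to Section 11.1, which holds adverse-event definitions.

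A reader might infer more than the documents support:

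- **That the trial's result is at risk.** The primary endpoint is confirmed shrinkage of a single non-irradiated lesion, and 9.5 allows it to coincide with progression. Neither that definition nor the Simon rule uses these lists.
- **That PFS, TTP and DCR are biased.** Section 12.2.2 bases PFS progression on RECIST 1.1. These endpoints are touched only if irRECIST is used to decide what counts as true progression, as the note in 9.6 suggests.
- **That counting combinations of findings measures the problem.** Such a count depends on how the combinations are drawn up and is unweighted. The documents give no basis for a number of patients.

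**Conclusion.** The lists in 9.2.2 are wrong as written. One clearly described scan falls in both, with opposite treatment plans, and another falls in neither. The rest of Section 9 points to the intended classifications, so the practical effect should be small. It is confined to site-level treatment and imaging decisions after a first RECIST 1.1 progression, with a conditional effect on PFS, TTP and DCR. Severity: minor.

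The conclusion rests on three assumptions. Tumor burden is the target-lesion sum, as in 9.6; 9.2.2 also tells investigators to consider non-target lesions, so the 25 mm bound holds only under this reading. A causal lesion is either worse or it is stable or improved. All relevant lesions are evaluated. How often either scan would occur cannot be estimated from the documents.

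**What to change.** Make three wording edits in 9.2.2.

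- **(a)** In the first condition of the not-progression list, follow the under-20% limit with *or < 5 mm absolute*, so that a rise below either threshold satisfies it.
- **(b)** Add a fourth condition to that list: no additional new lesion since the previous evaluation.
- **(c)** In the first progression item, replace *remains* with *is*, so that target growth first crossing 20% and 5 mm on the repeat scan is covered.

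With all three, the lists are exact complements and every evaluable repeat scan falls in exactly one. The result agrees with the 0.5 cm floor and the new-lesion rule in 9.6. The other progression items and the clinical-benefit exception stay as they are. Whether worsening of non-target disease that did not cause the first progression should count under irRECIST is a separate decision for the sponsor.

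The cost is a few words in one section, with no new scans or data collection and no change to the trial's stopping rules.

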9.5 Response criteria per best abscopal response

A novel aspect of this study is the examination of best abscopal response. Response criteria per best abscopal response are identical to RECIST-defined response criteria, with the exception that tumor shrinkage by > 20% in only a single representative measurable lesion (not a sum of lesions) is sufficient to count as a best abscopal response. In addition, up to 10 measurable lesions per organ may be recorded. Best abscopal response is a binary variable: present or not present. A subject can experience a best abscopal response at the same time as CR, PR, SD, or PD as defined by irRECIST/RECIST 1.1.

See 9.2.2 for guidance on management of cases when a best abscopal response co-occurs with PD as defined by irRECIST/RECIST 1.1.

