12.2 Endpoints

12.2.1 Definition of Primary Endpoint

The primary endpoint for this study will assess the confirmed response rate in the best responding abscopal lesion in a non-irradiated site. Best abscopal response is defined as the frequency of patients whose best responding abscopal lesion demonstrates at least a 30% decrease in its longest diameter from baseline (Golden et al., 2015). Responses need to be confirmed (2 consecutive responses at least 4 weeks apart) to count as a response (see Section 11). All eligible patients who are registered and start treatment will be evaluable for response.

The study is powered based on the confirmed response rate. In the largest second-line CUP trials where patients received cytotoxic therapy, patients received gemcitabine alone (N = 39) (Hainsworth et al., 2001) or gemcitabine plus irinotecan (N = 40) (Hainsworth et al., 2005). RRs were 8% and 10%, PFS was not reported, and OS was 3 months and 4.5 months—all respectively.

A Simon's optimal two-stage design will be utilized (see below). This design has 80% power to test the hypothesis of 15% improvement in RR (i.e. 24%) from a historical control of 9%, at one-sided significance level of 0.10. The 2-stage design details are below, where accrual will continue during the interim analysis phase unless we observe a much higher than expected accrual rate or toxicity rate.

Interim Analysis: Enroll 14 eligible patients. If at least 2 confirmed responses are observed in the first 14 eligible patients, we will continue the trial to the second stage and continue the study to a full accrual of 29 eligible patients. Otherwise, the study will be permanently closed due to lack of efficacy.

Final Analysis: If the trial is a success during the interim analysis, we will enroll another 15 eligible patients to the second and final stage (29 eligible total). If at least 5 confirmed responses are observed in the first 29 eligible patients (17%), the treatment will be considered worthy of further investigation. Otherwise, the study will be permanently closed due to lack of efficacy.

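### The rules for stopping imaging leave some abscopal responses seen at progression without an assured confirming scan, although only confirmed responses count for the primary endpoint

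*Combined protocol and SAP*

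**What the plan says.** **Endpoint.** Section 12.2.1 counts only responses seen on two consecutive assessments at least 4 weeks apart. All eligible patients who start treatment are in the denominator (12.2.1, 12.5), so a response without a second scan counts as a non-response. Section 9.1.1 asks for the second scan: "Best abscopal response should be confirmed by a repeat radiographic assessment not less than 4 weeks from the date the response was first documented". Section 9.5 adds: "A subject can experience a best abscopal response at the same time as CR, PR, SD, or PD as defined by irRECIST/RECIST 1.1".

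**Imaging.**
- Section 9.1: "Imaging should continue to be performed until whichever one of the following occurs first". The first item in the list that follows is disease progression, with no criterion named.
- Section 7, calendar footnote 6: tumor measurements run every 9 weeks, later less often, until the patient comes off study treatment.
- Section 9.2.2, table: after first RECIST 1.1 progression, a clinically stable patient has a repeat scan at 4 weeks or more. In a clinically unstable patient that scan is at the investigator's discretion. Once irRECIST progression is confirmed: "No additional scans required".
- Section 7, calendar: a CT is marked at the end-of-treatment visit. Footnote 13 places that visit 30 days (± 7) after the last dose.

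**The concern.** Section 1.2.2.3 explains why a lesion-level endpoint was chosen: mixed responses are expected, and RECIST alone may overlook patients who benefit. Section 9 also expects some responses to follow an apparent initial increase or new lesions. In such patients, shrinkage of one lesion may first be recorded on a scan that also shows progression, which is where the plan allows imaging to stop.

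If the confirming scan is not done, a genuine response is scored as a failure. Both decision points, 2 of 14 and 5 of 29, depend on a handful of responses. The risk is that an active regimen is discarded, not that an inactive one is accepted.

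**Working it through.** **1. Who is covered and who is not**

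| First scan showing the abscopal response | Next scan under the plan | Confirmation assured? |
|---|---|---|
| Before progression, with a second response scan at 4 weeks or more | Already done | Yes |
| First RECIST 1.1 progression scan, clinically stable | Repeat scan at 4 weeks or more (9.2.2) | A scan is assured, unless 9.1 is read literally and imaging stops at RECIST 1.1 progression |
| First RECIST 1.1 progression scan, clinically unstable | Discretionary (9.2.2) | No |
| Scan confirming irRECIST progression | None required (9.2.2) | No |

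The second row shows the conflict between 9.1 and 9.2.2. The last two rows are the gap with respect to 9.1.1.

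**2. Does the end-of-treatment CT fill the gap?**

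Let d be the days from the last dose to the scan on which the response first appears. The visit falls 30 − d days after that scan, with a window from 23 − d to 37 − d. Confirmation needs at least 28 days.
- At the nominal date: 30 − d ≥ 28, so d ≤ 2.
- At the latest permitted date: 37 − d ≥ 28, so d ≤ 9.
- With d = 21, one full cycle: nominally 30 − 21 = 9 days, window 2 to 16 days.

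The CT can therefore serve only when the scan closely follows the last dose. Footnote 6, which is attached to that calendar entry, also lists no end-of-treatment time point.

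**3. The plan's own design figures**

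Inputs from 12.2.1: continue on "If at least 2 confirmed responses are observed in the first 14 eligible patients"; succeed on 5 or more of 29; 24% tested "from a historical control of 9%, at one-sided significance level of 0.10", with 80% power.

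Probability of success at response rate p:

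S(p) = Σ (x = 2 to 14) C(14, x) pˣ (1 − p)¹⁴⁻ˣ × P[Bin(15, p) ≥ 5 − x]

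- S(0.09) = 0.0975, within 0.10.
- S(0.24) = 0.8058, against the stated 0.80.
- A search over two-stage designs returns 14/29 with these cut-offs as the optimal design.

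The stated figures reproduce. The margin over 80% is 0.6 percentage points.

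**4. Sensitivity range**

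Assumption, not in the documents: a share f of responders goes unconfirmed for lack of a scan, and the 24% did not already allow for this. The confirmed rate is then 0.24 × (1 − f).

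| f | Confirmed rate | Power | Stage 1 stop at true 24% | Type I error (9% cut by the same share) |
|---|---|---|---|---|
| 0 | 24.0% | 0.806 | 0.116 | 0.097 |
| 5% | 22.8% | 0.767 | 0.137 | 0.082 |
| 10% | 21.6% | 0.722 | 0.161 | 0.069 |
| 20% | 19.2% | 0.617 | 0.219 | 0.046 |

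For scale: 0.24 × 29 = 6.96 responders are expected, so one lost response is 1/6.96, about 14% of them.

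**The case against.** A reader might infer that imaging simply ends at progression, so that every mixed response becomes a non-response and power is below 80%. The documents do not support that.

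- **The main case is covered.** The repeat scan for stable patients has the same 4-week minimum as response confirmation. The cell quoted from 9.2.2 applies only after that scan. This stands.
- **Not required is not forbidden.** The table concerns confirmation of progression, and 9.1.1 asks for response confirmation without excepting progression. This stands as a reading. But a site that follows 9.1, the calendar and the table to the letter could skip the scan.
- **Provisions exist for this situation.** Footnote 1 of the table allows treatment to continue, after consultation, in a patient with confirmed progression and a responding non-irradiated lesion; scheduled scans would then go on. A CT is also marked at end of treatment. Both narrow the gap. The first is a discretionary exception that does not mention a confirming scan, and the second is timed from the last dose.
- **The 24% is already a confirmed rate.** Section 12.2.1 says the study is powered on the confirmed response rate. This stands: at a confirmed rate of 24% power is 0.806, and the lower figures hold only if that rate did not allow for missing scans.
- **The loss share is assumed, and the error is conservative.** Both points stand. Counting unconfirmed responses as failures is a defensible convention, provided it is known how many failures are only missing scans.

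**Conclusion.** The concern holds in a limited form. Section 9.1 leaves its progression criterion undefined and, read literally, contradicts the repeat scan in 9.2.2. Responses first seen on the scan confirming irRECIST progression, or on the first progression scan of a clinically unstable patient, have no assured scan 4 weeks later, although 9.1.1 asks for one and 12.2.1 requires it.

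The effect is a downward bias in the observed confirmed rate at both cut-offs. Its size cannot be derived, because the documents give no share of responders first detected at those scans. The range of 0.77 to 0.62 shows only how sensitive the design would be to losses of 5% to 20% under the assumption in step 4. It is not evidence that the plan misses its stated power. Type I error does not rise. The change is worth making because it is cheap and the decision rests on very few responses.

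**What to change.** 1. Reconcile sections 9.1, 9.1.1, the 9.2.2 table and calendar footnote 6. State in 9.1 that imaging for the primary endpoint ends at irRECIST-confirmed progression, subject to item 2.
2. Where an abscopal response is first recorded on the scan that would end imaging, time the calendared end-of-treatment CT at least 4 weeks after that scan, so that it serves as the 9.1.1 confirming scan. Apply this where feasible and unless new systemic anticancer therapy has started. List this CT in footnote 6.
3. Keep unconfirmed responses as non-responses in the primary analysis, and report how many were unconfirmed for lack of a scan.

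The cost is wording and an occasional off-treatment scan that 9.1.1 already requests. The cut-offs, sample size and treatment rules do not change. The scan will still be missing in patients who start new therapy first or are too unwell, which is why item 3 is needed.
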